- j Subjects are required to dose at the clinic on Day 1 – 14 as dilution of dose is required by site staff. Subjects are also required to dose at the clinic on study day visits when predose assessments are required.
- k On Day 14, the subject will receive a final 50 μ g dose; on Day 15 subjects will receive a 100- μ g dose of IP, and should be discharged home with adequate supply of IP for a further 13 days of dosing at the 100- μ g dose level. On Day 29, subjects should receive a 200- μ g dose during their study visit, and again be discharged with 13 days supply of IP for dosing at the 200- μ g dose level. On Day 43, subjects should receive a 300- μ g dose during their study visit and continue this dose until the end of the study.
- l Predose not applicable on Days 7, 15, 29, and 43. An additional blood test for safety (to be taken at any time between Day -3 and Day -7) is not required if the screening visit occurs within 7 days of dosing (Day 1); if the screening visit is more than 7 days prior to dosing on Day 1 then additional safety blood tests should be taken (as described in Section 4.3.3).
- m PK Sampling Schedule for MED10382:
Day -1: No specific time point
Day 1: Predose, 1, 2 (\pm 15 min); 4, 6, 8, and 12 (\pm 30 min) hours postdose
Day 2: Predose
Day 7: Predose, 1, 2 (\pm 15 min); 4, 6, 8, and 12 (\pm 30 min) hours postdose
Day 8: Predose (\pm 15 min)
Day 14: Predose, 1, 2 (\pm 15 min); 4, 6, 8, and 12 (\pm 30 min) hours postdose
Day 15, 29, 43, 49, 50; Predose
- n MMTT Schedule (Type A and Type B): Following a minimum 10-hour fast overnight and 2.5 hours after taking the IP, a blood sample for glucose (Type B) or a glucose metabolism panel [REDACTED] will be taken immediately (within 15 minutes) prior to the subject drinking 1 entire can of Ensure Plus as a standardised meal (ie, “0 minutes”). Blood samples for glucose metabolism panel will

additionally be drawn at 5, 10, 15, 30, 45, 60, 90, 120, 180, and 240 minutes (\pm 5 minutes) after consumption of the standardised meal. The same procedure and schedule applied to MMITT with glucose only measurements.

- o ADA Sampling Schedule: Day 1 predose; Day 29 predose; Day 50 predose; and 28 days after administration of the last dose in the study.

p [REDACTED]

- q Subjects should fast for > 10 hours the night before; in the morning, 2.5 hours postdose (except for the baseline measurement), a baseline blood test for glucose and insulin should be taken alongside a baseline measurement of expired CO₂ just prior to administration of the C¹³-octanoate in conjunction with a standardised solid meal. Subjects will be expected to consume the meal within less than 5 minutes and may be required to be on bed rest until the final breath sample is taken. Collection of expired CO₂ should occur as described in the detailed methods section (Section 4.3.6.1). Where indicated, concurrent blood sampling of glucose and insulin should be performed at t = 0 (baseline), t = 30 min, t = 60 min, t = 120 min and t = 240 min (\pm 5 min) after taking the standardised meal.

r [REDACTED]

- s A glucometer, test strips, and a diary should be provided to the subject. The subject should be trained in its use and advised to test their capillary blood glucose at any time the subject feels unwell or has symptoms of hypoglycaemia (hunger, dizziness, shaking, sweating, or irritability).

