
To assess gastrointestinal (GI) tolerability across different titration schedules (Cohorts 1 and 2)
	
 • Percentage of subjects with GI AEs at each dose level • Percentage of subjects with nausea and vomiting from baseline (Day 1) over 7 days of treatment

To assess the effect of MEDI0382 on glucose lowering during different meals and times of the day as measured by continuous glucose monitoring (CGM) (Cohort 1 only)
	
 • Change in glucose AUC_{24h} from baseline (Day -1) to the end of dosing at each dose level (Days 7, 14, 21, 28, and 49) • Change in coefficient of variation (ratio of standard deviation: mean) over 24 hours from baseline (Day -1) to the end of dosing at each dose level (Days 7, 14, 21, 28, and 49) • Change in coefficient of variation (ratio of standard deviation: mean) over 7 days at each dose level (Days 1 to 7, Days 8 to 14, Days 15 to 21, and Days 22 to 28) • Change in percentage of time in hyperglycaemia (defined as > 7.8 mmol/l (> 140 mg/dl) and hypoglycaemia (defined as < 3.0 mmol/l (< 54 mg/dl) from baseline (Day-1) over 24 hours to the end of dosing at each dose level (Days 7, 14, 21, 28, and 49) • Change in percentage of time in hyperglycaemia; (defined as > 7.8 mmol/l or (> 140 mg/dl) and hypoglycaemia (defined as < 3.0 mmol/l or < 54 mg/dl) over 7 days at each dose level (Days 1 to 7, Days 8 to 14, Days 15 to 21, and Days 22 to 28) • Change in glucose AUC_{120min} during a standardised meal in the morning from baseline (Day -1) and at the end of 49 days of treatment • Change in glucose AUC_{120min} during a standardised meal in the evening from baseline (Day -1) and at the end of 49 days of treatment

To characterise the effect of MEDI0382 on glucose lowering and weight versus placebo after 7, 14, and 49 days (Cohort 2 only)
	
 • Percentage change in glucose AUC as measured by a standardised MMTT from baseline (Day -1) after 14 and 49 days • Change in fasting plasma glucose from baseline (Day -1) to the end of 7, 14, and 49 days of treatment • Percentage and absolute change in body weight from baseline (Day 1) to the end of 7, 14, and 49 days of treatment • Change in HbA1c from baseline (Day -1 to the end of 49 days of treatment

[REDACTED]
	
[REDACTED]

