2.3 Exploratory Objectives

Table 2.3-1 Exploratory Objectives and Associated Endpoints

Type	Objective	Endpoint
Safety	To assess gastrointestinal tolerability across different titration schedules (Cohorts 1 and 2)	
 Percentage of subjects with gastrointestinal AEs at each dose level Percentage of subjects with nausea and vomiting from baseline (Day 1) over 7 days of treatment
PD	To assess the effect of MEDI0382 on glucose lowering during different meals and times of the day as measured by continuous glucose monitoring (CGM) (Cohort 1 only)	
 Change in percentage of time in hyperglycaemia (defined as > 7.8 mmol/l or > 140 mg/dl) and hypoglycaemia (defined as < 3 mmol/l or < 54 mg/dl) from baseline (Day -1) over 24 hours to the end of dosing at each dose level (Days 7, 14, 21, 28, and 49) Change in percentage of time in hyperglycaemia (defined as > 7.8 mmol/l or > 140 mg/dl) and hypoglycaemia (defined as < 3 mmol/l or < 54 mg/dl) over 7 days at each dose level (Days 1 to 7, Days 8 to 14, Days 15 to 21, and Days 22 to 28) Change in glucose AUC_{120min} during a standardised meal in the morning from baseline (Day -1) and at the end of 49 days of treatment Change in glucose AUC_{120min} during a standardised meal in the evening from baseline (Day -1) and at the end of 49 days of treatment
Efficacy	To characterise the effect of MEDI0382 on glucose lowering and weight versus placebo after 7, 14 and 49 days (Cohort 2 only)	
 Percentage change in glucose AUC as measured by a standardised MMTT from baseline (Day -1) after 14 and 49 days Change in fasting plasma glucose from baseline (Day -1) to the end of 7, 14, and 49 days of treatment Percentage and absolute change in body weight from baseline (Day 1) to the end of 7, 14, and 49 days of treatment Change in HbA1c from baseline (Day -1) to the end of 49 days of treatment

Table 2.3-1 Exploratory Objectives and Associated Endpoints

Type	Objective	Endpoint
PD	To assess the effect of MEDI0382 on ketone bodies, amino acids, and free fatty acid (FFA) levels over 49 days of treatment (Cohort 1 only)	
 Change in plasma beta-hydroxybutyrate from baseline (Day -1) while fasted and at 4 hours postdose after 49 days Change in FFA levels from baseline (Day -1) after 49 days of treatment Change in amino acid levels from baseline (Day -1) after 49 days of treatment

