 - o Day 1; vital signs to be taken; predose (-15 min), 15, 30, and 60 minutes (\pm 5 min) and 2 hours (\pm 10 min) postdose

- o Day 7, 15; 23 no specific time point
 - o Day 22, 29, 36, and 43; vital signs to be taken prior to fitting ABPM device
 - o Day 49: vital signs to be taken prior to fitting the ABPM device; postural (standing and supine) blood pressures should be performed at this time.
- f Subjects will be fitted with the ABPM device while at the clinical unit, which may involve practice inflations. The ABPM device should be applied on the opposite arm to the arm where the CGM device is applied. The subject will then wear the monitor/cuff for approximately 24 hours (including overnight at home) and will remove the device at home at the end of the 24-hour period. Subjects will return the device to the clinic.
- g A single digital ECG recording should be performed predose after the subject has rested for 10 minutes in the supine position on Day 1, 7, 22, and 49. No specific time point for other visits.
- h Body weight should be measured in the morning prior to breakfast (predose on Day 1); the subject should take off their shoes and remove bulky clothing. Calibrated scales should be used.
- i Randomisation may occur any time from Day -1 to Day 1 predosing.
- j Subjects are required to fast overnight on the night of Day -2, -1, 6, 21, 48, and 49. Refer to footnote (s) for additional fasting requirements on Day -2 and Day 49 during the day.
- k Subjects are required to dose at the clinic on Day 1 – 7 as dilution of dose is required by site staff. Subjects are also required to dose at the clinic on study day visits when predose assessments are required. See Section 4.5.1.3 for further information.
- l On Day 7, the subject will receive a final 50-µg dose, and should be provided with 7 days of IP supply to dose at the 100-µg dose level and advised to commence this dose level on Day 8 while they are at home. On Day 15, subjects will be given a 200-µg dose during their study visit, and should be provided with 6 days IP supply for dosing at the 200-µg dose level while at home. Subjects should be given the first 300-µg dose on Day 22 and continue this dose level for the remainder of the study.

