^u CGM sensor application should occur at approximately 1200 hours on Day -2; thereafter, existing CGM sensors should be removed and a new sensor applied at 1200 hours \pm 20 minutes on Days 7 and at any time on Day 36. On Day 22, the old sensor should be removed and a new sensor applied predose and ideally should be the first study procedure performed at that visit. If the sensor fails, or needs to be replaced, it should be re-applied as soon as possible. The CGM sensor should be removed after 0800 hours on Day 50. Whenever a new CGM sensor is applied, at least 1 hour afterwards, the site staff should place the monitor in close proximity with the sensor to transfer data and ensure that the sensor and monitor are functioning adequately.

^v A glucometer, test strips, and a diary should be provided to the subject. The subject should be trained in its use and advised to test their capillary blood glucose at any time the subject feels unwell or has symptoms of hypoglycaemia (hunger, dizziness, shaking, sweating, or irritability).

Table 4.2.2-2 Schedule of Treatment Period Study Procedures: Cohort 2

Study Period	Inpatient		Inpatient or daily visits	Inpatient		Inpatient or daily visits	Inpatient		Inpatient or daily visits	Outpatient		Outpatient	
	-2	-1		1	2-6		7	8		9-13	14		15
Visit Number	V2		V3		V4		V5		V6		V7		V8
Procedure													
Verify eligibility criteria ^a		X											
Admit to clinical unit ^b	X				X							X	
Discharge from clinical unit ^c				(X) (D2)		(X)			X				X
Outpatient visit to clinic ^c				(X)						X			X
Medical and disease history	X												
Pregnancy test (if applicable) ^d	X								X			X	
Targeted physical examination	X				X				X		X	X	
Vital signs (BP, heart rate, body temperature, RR) ^e	X		X		X	X		X	X	X	X	X	X
ECG ^f			X		X				X		X	X	
Body weight ^g			X								X	X	
SC injection training	X	X	X										
Randomisation ^h		X											
Subject required to fast overnight for 10 hours ⁱ	X (D-3 and D-2)	X		X (D6)			X (D13)	X		X (D28)	X (D42)	X (D48 and D49)	
IP administration ^j			X	X	X	X							
Up-titration ^k									X	X	X		
Collect blood for:									X	X	X		

Table 4.2.2-2 Schedule of Treatment Period Study Procedures: Cohort 2

Study Period	Inpatient		Inpatient or daily visits		Inpatient		Inpatient or daily visits		Inpatient		Outpatient		Inpatient		Outpatient	
	-2	-1	1	2-6	7	8	9-13	14	15	29	43	49	50	7 to 14 Days Post Last Dose		
Study Day																

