4.3.6.2 Training for Application and Wearing of CGM Sensor

A Freestyle Libre[®] Pro CGM device will be used to measure interstitial glucose levels during the study. The Freestyle Libre[®] Pro CGM device measures interstitial glucose levels every 15 minutes for 2 weeks continuously, and does not require any calibration or periodic near-touch/ blue-tooth connections with the device to perform this function. The Freestyle Libre[®] Pro CGM device does not permit flash glucose measurements. Study site staff and investigators should avoid periodic reviews of interstitial glucose levels during the study to avoid the risk of unblinding. However, should a subject experience an AE or SAE, and the investigator deems information acquired by CGM to be useful in the subject's ongoing management, interstitial glucose readings may be reviewed by the investigator as described in the manual, and should avoid review of baseline readings taken on Day-2 and Day -1. The CGM sensor, which is a small plastic circular device of 35 mm diameter and 5 mm depth, should be applied to the back of the upper arm, taking into account subject preference and the side where the ABPM device will be sited. The selected site should be shaved where necessary, and a sterile alcohol wipe supplied with the kit used to clean the site prior to application. Study site staff should refer to the training materials and manual for application of the CGM sensor. Subjects will be expected to wear the CGM sensor continuously up until the time of a sensor change, which should occur within 14 days, and are to be advised that they may bathe and shower, and swim in up to 3 m depth for up to 30 minutes while wearing the CGM sensor. The CGM sensor should be removed at the specified times in the schedule of assessments (CGM sensor change). At this time the site should be inspected and cleaned; and a new CGM sensor may be reapplied ideally close to the original site, but taking into account the subject's preference on site. CGM sensors are single-use only and cannot be reapplied once removed and may only be applied to the upper arm and not to any other site in the body. It should be noted that monitors should remain at the study site and not be provided to subjects to take home.

If a subject is unable to tolerate wearing the CGM sensor for the entire duration of the study, the sensor should be removed; but the subject should remain in the study with or without continued CGM.

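### Cohort 1 CGM: the Day 7 to Day 22 sensor interval exceeds the 14-day sensor life, so recording ends about midday on Day 21, and the Day 7 change can fall inside the meal test

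*Protocol*

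**What the plan says.** Protocol Table 4.2.2-1 footnote u schedules four sensor applications for Cohort 1. The first is at about noon on Day -2. On Day 7, "existing CGM sensors should be removed and a new sensor applied at 1200 hours", with a tolerance of 20 minutes. Then "On Day 22, the old sensor should be removed and a new sensor applied predose". The fourth is at any time on Day 36, with removal after 0800 on Day 50. The table itself asks for continuous wear until Day 50.

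Protocol Section 4.3.6.2 says the device "measures interstitial glucose levels every 15 minutes for 2 weeks continuously" and that a sensor is worn "up until the time of a sensor change, which should occur within 14 days". It adds that "monitors should remain at the study site and not be provided to subjects to take home".

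Footnote l starts 200 µg at the Day 15 visit, where the subject "should be provided with 6 days IP supply for dosing at the" same level at home; 300 µg starts on Day 22. Day 21 is therefore the last 200 µg day, and it is spent at home.

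The Synopsis defines the 24-hour CGM endpoints (AUC, coefficient of variation, percentage of time in hyper- and hypoglycaemia) as changes from Day -1 "to the end of dosing at each dose level (Days 7, 14, 21, 28, and 49"). Table 2.3-1 repeats this for percentage of time: "over 24 hours to the end of dosing at each dose level (Days 7, 14, 21, 28, and 49"). SAP 3.5.1.1 also lists 7-day measures, one of them for Days 15 to 21, and a CGM AUC over 0-4 hours during the Day 7 Type B meal test.

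**The concern.** The sensor interval and the sensor life come from the same protocol and do not fit together. The shortfall falls at the end of the 200 µg step, where the CGM endpoints are meant to be read. On a calendar-day window the 200 µg value would rest on night and morning hours only, while the other four dose-level days include afternoon and evening meals.

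Under SAP 3.5.1.2 the Day 21 24-hour values are summarised but not tested. The 7-day coefficient of variation (t-test) and percentage of time (Wilcoxon) are tested at each dose level, so the Days 15-21 tests would run without the last afternoon and evening in both arms. SAP 3.1 applies LOCF to pharmacodynamic endpoints unless otherwise specified. If a partial Day 21 were treated as missing, Day 14, a 100 µg day, could be carried into the 200 µg row.

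The Day 7 change raises a second problem. SAP 3.5.1.2 compares CGM and plasma AUC over 0-4 hours by paired t-test and concordance correlation. A sensor swap during the meal makes the CGM side a splice of two sensors, possibly with a short gap.

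**Working it through.** **Inputs.** Sensor life 14 days = 336 h, one reading per 15 minutes (Section 4.3.6.2), so 96 readings per day and 7 × 96 = 672 per week. Day 7 change at 1200 ± 20 min and Day 22 change before the dose (footnote u). Meal 2.5 h after the dose (footnote r), sampling to 240 min (Section 4.3.1.1). Dosing is in the morning, with no clock time given; 0600 to 1000 is assumed for the Day 22 change.

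**Expiry of the Day 7 sensor.** Day 7 1200 + 14 d = Day 21 1200 (1140 to 1220 with the tolerance).

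**Interval to the Day 22 change, for a 1200 change on Day 7:**

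| Day 22 change | Interval | Excess over 14 d |
|---|---|---|
| 0600 | 14 d 18 h | 18 h |
| 0800 | 14 d 20 h | 20 h |
| 1000 | 14 d 22 h | 22 h |

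The shortest interval that could be argued for, Day 7 1220 to Day 22 0000, is 14 d 11 h 40 min. No permitted timing meets 14 days.

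**Readings lost (assumed windows, as neither document defines the 24-hour bounds):**

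- Midnight to midnight: 12 h × 4 = 48 readings. Day 21: 48/96 = 50%. Days 15-21: 48/672 = 7.1%.
- Dose to dose: 18 to 22 h × 4 = 72 to 88 readings. Day 21: 72/96 to 88/96 = 75% to 92%. Days 15-21: 72/672 to 88/672 = 10.7% to 13.1%.

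**Other named days.** With changes at Day -2 1200, Day 7 1200, Day 22 0800 and Day 36 0800, calendar Days -1, 14, 28 and 49 each fall within the life of a single sensor. Day 7 is spanned by two sensors, apart from any short gap at the swap. Day 21 is the only named day that the schedule leaves half uncovered.

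**Day 7 meal test.** The test runs from dose + 2.5 h to dose + 6.5 h.

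- It contains 1200 when the dose is between 12:00 − 6:30 = 0530 and 12:00 − 2:30 = 0930.
- The whole 1140-1220 tolerance lies inside for doses from 12:20 − 6:30 = 0550 to 11:40 − 2:30 = 0910.
- There is no overlap only for doses before 11:40 − 6:30 = 0510 or after 12:20 − 2:30 = 0950.
- For doses at 0700, 0800 and 0900, a noon change comes 150, 90 and 30 minutes after the meal.

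**The case against.** The strongest reply is that little depends on this. All affected endpoints are exploratory, the Day 21 24-hour values are not tested, and Day 49, which is, is covered. The tested Days 15-21 measures keep about 93% of their readings on a calendar window, retain six of seven afternoons and evenings, and lose the same hours in both arms. No bias in those tests has been shown. This stands, and it limits the weight of the point.

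The percentages depend on assumed windows. SAP 3.5.1.1 speaks only of the end of each dosing level, and a 24-hour window ending at noon on Day 21 would be complete. The SAP also refers to a statistical programming plan that may define one. But the protocol names Day 21, and neither document states such a window.

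The LOCF consequence needs a partial day to be declared missing and LOCF to be applied to a by-visit summary. The SAP states neither, so this is a possibility only.

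That recording stops at exactly 336 h is inferred from the stated two-week life. Footnote u also allows replacement when a sensor fails or needs it, which a site could use on Day 15. That clause schedules nothing, however. Cohort 1 has no visit between Day 15 and Day 22, and the monitors stay on site.

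The Day 7 overlap depends on a dose time that is not given; a dose after 0950 avoids it. It does not touch the plasma glucose AUC.

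**Conclusion.** The concern holds. Followed as written, the schedule exceeds the protocol's own 14-day limit by 11 h 40 min at the very least, and by 18 to 22 h for a Day 22 change between 0600 and 1000. It removes the same part of Day 21 from every Cohort 1 subject whose sensor was not replaced early. The loss is half of a calendar Day 21, or 75-92% of a dose-to-dose Day 21, and 7% or 11-13% of Days 15-21 respectively. This rests on recording ending at two weeks and on the assumed change times and windows.

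The Day 7 meal-test overlap is conditional, but it occurs for any dose from 0530 to 0930 with a noon change.

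The co-primary and secondary endpoints do not use CGM and are unaffected. The point should be corrected because the loss is systematic and avoidable and falls on the only end-of-200-µg day.

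**What to change.** **Protocol footnote u.** Place the Day 7 change after the 240-minute meal-test sample, and bring the Day 7 to Day 22 interval within 14 days, for example by a change at the existing Day 15 visit. Moving the Day 7 change alone is not enough. For an 0800 dose the test ends at 1430, so that sensor expires at 1430 on Day 21 and 9.5 h of the day are still lost. With an added change at 0800 on Day 15, the intervals become 7 d 17.5 h and 7 d.

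**SAP, if no change is added.** Define the end-of-200-µg window as the last complete 24 h of sensor life: recorded Day 7 application time + 13 d to + 14 d (1200 on Day 20 to 1200 on Day 21 for a noon change). Compare it with the full calendar Day -1, which lies after the first application and before the first dose. Both windows contain every clock hour, so no clock matching is needed.

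**SAP, in either case.** State the 24-hour window. Set a minimum number of valid readings out of 96 for a day and out of 672 for a week. Do not carry a CGM value forward from one dose level to another. Carrying Day 28 to Day 49 would remain possible, as both are at 300 µg.

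**Cost.** The SAP text costs almost nothing. A Day 15 change raises scheduled sensors from 4 to 5 per subject, 39 more for the 39 planned subjects, with no new visit. It does bring footnote u's wait of at least one hour for the function check into that visit, and puts a sensor swap at the start of the Days 15-21 window. A substantial protocol change also needs ethics committee approval before use (Section 7.4).

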4.2.3 Follow-up Period

Table 4.2.3-1 shows all procedures to be conducted during the follow-up period.

Whenever vital signs, 12-lead ECGs, and blood draws are scheduled for the same nominal time, the assessments should occur in the following order: 12-lead ECG, vital signs, and then blood draws.

After the end of the follow-up period, subjects will return to the care of their own physicians according to local requirements and local standards.

Table 4.2.3-1 Schedule of Follow-up Procedures

Study Period	Follow-up Period
Visit Number	Final
Procedure/Study Day	28 days post last dose (\pm 3 days)
Targeted physical examination	X
Weight	X
ECG	X
Vital signs (BP, heart rate, body temperature, RR) ^a	X
ABPM (Cohort 1 only)	X
	
Serum chemistry panel	X
Fasting lipid profile	X
Calcitonin ^c	X
Haematology	X
Urinalysis	X
HbA1c	X
Pregnancy test	X
MEDI0382 ADA ^d	X
Assessment of AEs/SAEs	X
Concomitant medications	X

ABPM = ambulatory blood pressure monitoring; AE = adverse event; ADA = anti-drug antibody; BP = blood pressure; ECG = electrocardiogram; HbA1c = glycated haemoglobin; min = minute; RR = respiration rate; SAE = serious adverse event; ULN = upper limit of normal

- ^a Blood pressure should be measured once at heart level in the nondominant arm where possible, after the subject has rested in either a seated or supine position for at least 10 minutes.
- ^b Subjects should fast for > 10 hours the night before; in the morning, a baseline blood test for glucose and insulin should be taken alongside a baseline measurement of expired CO₂ just prior to administration of C¹³- octanoate in conjunction with a standardised solid meal. Subjects will be expected to consume the meal within less than 5 minutes. Blood sampling of glucose and insulin should be performed at t = 0

Table 4.2.3-1 Schedule of Follow-up Procedures

Study Period	Follow-up Period
Visit Number	Final
Procedure/Study Day	28 days post last dose (± 3 days)

(baseline), t = 30 min, t = 60 min, t = 120 min and t = 240 min (± 5 min) after taking the standardised meal. Concurrent sampling of expired CO₂ should occur as described in the detailed methods section.

^c Only to be repeated if the calcitonin level was > ULN in the sample taken at the end of dosing

^d If this sample is ADA positive, the subject will be asked to return to provide another sample at approximately 3 months after the end-of-study visit (post-study sample). If the sample taken at 3 months is ADA positive, the subject will be asked to return to provide a sample in another 3 months

